11.1.5 Serious Adverse Event Reporting

In the event of a serious adverse event, and additionally, any non-serious event of malignancy in patients 30 years of age and younger, whether related to study drug or not, the Investigator will notify the AbbVie contact identified in section 11.1.5 within 24 hours of the site being made aware of the event by entering the serious adverse event or non-serious event of malignancy in patients 30 years of age and younger data into the electronic data capture (EDC) system. Serious adverse events and non-serious events of malignancy in patients 30 years of age and younger, that occur prior to the site having

access to the EDC system or if the EDC system is not operable should be faxed/e-mailed to the AbbVie contact identified in section 11.1.5 within 24 hours of being made aware of the adverse event.

In the event of a serious adverse event, the physician will:

- For events from patients using and AbbVie product notify the AbbVie contact person identified below within 24 hours of the physician becoming aware of the event.
- For events from patients using a comparator product notify the Marketing Application Holder (MAH) for the comparator product within 24 hours of the physician becoming aware of the event.

Contact details for event reporting:

E-mail:		
Phone:		
Fax:		

As the safety profile of Adalimumab is stable and well established, non-serious events will not be actively solicited as these events are not likely to further contribute to the understanding of the safety profile of the product. Any non-serious reports will be collected as spontaneous reports if notified to AbbVie.

11.1.6 Pregnancy Reporting

In the event of a pregnancy occurrence in the patient, the physician will notify AbbVie contact identified in Section 11.1.5 within 24 hours of the physician becoming aware of the pregnancy.

11.2 Product Complaint

11.2.1 Definition

A Product Complaint is any Complaint (see Section 11.0 for the definition) related to the biologic or drug component of the product or to the medical device component(s).

For a product this may include, but is not limited to, damaged/broken product or packaging, product appearance whose color/markings do not match the labeling, labeling discrepancies/inadequacies in the labeling/instructions (example: printing illegible), missing components/product, device not working properly, or packaging issues.

For medical devices, a product complaint also includes all deaths of a patient using the device, any illness, injury, or adverse event in the proximity of the device, an adverse event that could be a result of using the device, any event needing medical or surgical intervention including hospitalization while using the device and use errors.

Any information available to help in the determination of causality by the device to the events outlined directly above should be captured.

11.2.2 Reporting

Product Complaints concerning the investigational product and/or device must be reported to the Sponsor within 24 hours of the study site's knowledge of the event via local Product Complaint reporting practices. Product Complaints occurring during the study will be followed-up to a satisfactory conclusion. All follow-up information is to be reported to the Sponsor (or an authorized representative) and documented in source as required by the Sponsor. Product Complaints associated with adverse events will be reported in the study summary. All other complaints will be monitored on an ongoing basis.

Product complaints involving a non-Sponsor investigational product should be reported to the identified contact or manufacturer, as necessary per local regulations.

Product Complaints may require return of the product with the alleged complaint condition (syringe, pen, etc.). In instances where a return is requested, every effort should be made by the investigator to return the product within 30 days. If returns cannot be accommodated within 30 days, the site will need to provide justification and an estimated date of return.

The description of the complaint is important for AbbVie in order to enable AbbVie to investigate and determine if any corrective actions are required.
12.0 Plans for Disseminating and Communicating Study Results

Core publication(s) will be authored by Principal Investigator(s) specified by AbbVie who contribute significantly to the implementation and conduct of the study and non-site personnel who contribute substantially to the design, interpretation or analysis of the study (e.g., AbbVie personnel or consultants). AbbVie scientists making significant contributions to the study will be included in the list of authors.

Development of the core publication will be coordinated by a publication committee, whose membership will include investigators who provided significant input into study design, implementation, conduct and interpretation, in addition to AbbVie scientific personnel responsible for study conduct.

At the end of the study, AbbVie will write a study report. This report will contain a description of the objectives of the PMOS, the methodology of the study, its results and conclusions.

The completed case report forms, questionnaires and the study report are the confidential property of AbbVie and may not be released to unauthorized people in any form (publications or presentations) without express written approval from AbbVie. The results of this PMOS may be published by AbbVie or by any one of the participating Investigators after agreement with AbbVie.

Appendix 1. Dermatology Life Quality Index (DLQI) – Example

The aim of this questionnaire is to measure how much your skin problem has affected your life OVER THE LAST WEEK. Please check $\sqrt{}$ one box for each question.

Qu	estion	Response				
1.	Over the last week, how itchy, sore, painful or stinging has your skin been?	Very much				
		A little				
		Not at all				
2.	Over the last week, how embarrassed or self conscious have	Very much				
	you been because of your skin?	A lot				
		A little				
		Not at all				
3.	Over the last week, how much has your skin interfered with you	Very much				
	going shopping or looking after your home or yard?	A lot				
		A little				
		Not at all	Not relevant			
4.	Over the last week, how much has your skin influenced the	Very much				
	clothes you wear?	A lot				
		A little	_			
		Not at all	Not relevant			
5.	Over the last week, how much has your skin affected any social or leisure activities?	Very much				
	or leisure activities?	A lot				
		A little	_			
		Not at all	Not relevant			
6.	Over the last week, how much has your skin made it difficult	Very much				
	for you to do any sport?	A lot				
		A little	_			
		Not at all	Not relevant			

7.	Over the last week, has your skin prevented you from working	yes	
	or studying?	no	Not relevant 🗌
	If "No", over the last week how much has your skin been a	A lot	
	problem at work or studying?	A little	
		Not at all	
8.	Over the last week, how much has your skin created problems	Very much	
	with your partner or any of your close friends or relatives?	A lot	
		A little	
		Not at all	Not relevant
9.	Over the last week, how much has your skin caused any sexual	Very much	
	difficulties?	A lot	
		A little	
		Not at all	Not relevant
10.	Over the last week, how much of a problem has the treatment	Very much	
	for your skin been, for example by making your home messy, or	A lot	
	by taking up time?	A little	
		Not at all	Not relevant

Please check you have answered EVERY question. Thank you.

⁰ AY Finlay, GK Khan, April 1992, This must not be copied without the permission of the authors.

Appendix 2. Patient's Global Assessment of Skin Pain – NRS – Example

Please mark an "X" in the box (X) which best describes the severity of your skin pain in the last 7 days.

Appendix 3 EuroQol (EQ-5D) – Example

By placing a checkmark in one box in each group below, please indicate which statements best describe your own health state today.

Mobility	
I have no problems in walking about	
I have some problems in walking about	
I am confined to bed	
Self-Care	
I have no problems with self-care	
I have some problems washing or dressing myself	
I am unable to wash or dress myself	
Usual Activities (e.g., work, study, housework, family or leisure activitie	25)
I have no problems with performing my usual activities	
I have some problems with performing my usual activities	
I am unable to perform my usual activities	
Pain/Discomfort	
I have no pain or discomfort	
I have moderate pain or discomfort	
I have extreme pain or discomfort	
Anxiety/Depression	
I am not anxious or depressed	
I am moderately anxious or depressed	
I am extremely anxious or depressed	
[©] 1998 EuroQol Group. EQ-5D™ is a trade mark of the EuroQol Group	

To help people say how good or bad a health state is, we have drawn a scale (rather like a thermometer) on which the best state you can imagine is marked 100 and the worst state you can imagine is marked 0.

We would like you to indicate on this scale how good or bad your own health is today, in your opinion. Please do this by drawing a line from the box below to whichever point on the scale indicates how good or bad your health state is today.

> Your own health state today

Bact integinable health state

สร้า ระชาร์ ระระการที่นานหนึ่งหนุ่มหรือการที่หน่าน รู้ แปลา รู้ แปลามรู้ แปลามรู้ แปลายรู้ แปลายรู้แปลาไทย รู้ ระชาร์

 $^{\textcircled{0}}$ 1998 EuroQol Group. EQ-5
D^w is a trade mark of the EuroQol Group

Appendix 4 Hidradenitis Suppurativa Impact Assessment (HSIA) – Example

Instructions: This questionnaire includes 18 questions about the impacts that you may experience associated with your Hidradenitis Suppurativa (HS). Hidradenitis Suppurativa is a skin condition that affects areas with sweat glands such as the underarms, breasts, inner thighs, groin, and buttocks. People often refer to their HS as boils, cysts, or lesions on their skin.

Please clearly mark an "x" in the box (X) that best describes how you have been affected by your HS in the past 7 days. There are no right or wrong answers to any of the questions.

1. Over the past 7 days, how uncomfortable did your clothing make you feel because of your HS?

2. Over the past 7 days, how hard was it for you to move your arms because of your HS?

 Over the past 7 days, how hard was it for you to exercise (for example, play sports, work out) because of your HS?

Note: If you did not exercise because of your HS please mark a "10".

4. Over the past 7 days, how hard was it for you to walk because of your HS?

Note: If you did not walk because of your HS please mark a "10".

5. Over the past 7 days, how hard was it for you to sit because of your HS?

Note: If you did not sit down because of your HS please mark a "10".

6. Over the past 7 days, how much did your HS interfere with your wanting to be around other people (for example, going to a party, being with friends or family)?

7. Over the past 7 days, how much did your HS interfere with your ability to do things around the house (for example, cleaning, cooking, yard work)?

8. Over the past 7 days, how self-conscious did you feel because of your HS?

13. Over the past 7 days, how much did your feelings about your HS limit your desire to have sex (for example, because you felt unattractive, embarrassed, self-conscious, etc.)?

14. Over the past 7 days, how much was your ability to have sex limited because of your HS symptoms (for example, pain, cysts, drainage, flare ups, bleeding, etc.)?

15. Over the past 7 days, how satisfied have you been with your HS medications?

16. Over the past 7 days, how bothered did you feel by the scars from your past HS surgery/surgeries?

- 17. Over the past 7 days, how many hours did you spend at work or school?
 - Hours

 Over the past 7 days, how many hours did you miss from work or school because of your HS? Include hours you missed on sick days, times you went in late, left early, etc., because of your HS.

Hours

Not applicable. I am not employed nor do I attend school

Appendix 5 Work Productivity and Activity Impairment Questionnaire: Specific Health Problem (WPAI:SHP) - Example

The following questions ask about the effect of your hidradenitis suppurativa on your ability to work and perform regular activities. *Please fill in the blanks or circle a number, as indicated.*

 Are you currently employed (working for pay)? _____ NO ___ YES If NO, check "NO" and skip to question 6.

The next questions are about the past seven days, not including today.

2. During the past seven days, how many hours did you miss from work because of problems associated with your hidradenitis suppurativa? Include hours you missed on sick days, times you went in late, left early, etc. because of your hidradenitis suppurativa. Do not include time you missed to participate in this study.

___HOURS

3. During the past seven days, how many hours did you miss from work because of any other reason, such as vacation, holidays, time off to participate in this study?

HOURS

4. During the past seven days, how many hours did you actually work?

HOURS (If "0," write "0" and skip to question 6.)

 During the past seven days, how much did hidradenitis suppurativa affect your productivity while you were working?

Think about days you were limited in the amount or kind of work you could do, days you accomplished less than you would like, or days you could not do your work as carefully as usual. If hidradenitis suppurativa affected your work only a little, choose a low number. Choose a high number if hidradenitis suppurativa affected your work a great deal.

Hidradenitis											Hidradenitis	
suppurativa had no effect on my work	0	1	2	3	4	5	6	7	8	9	10	suppurativa completely prevented me from working
				C	IRCL	EA	NUM	IBEF	2			

6. During the past seven days, how much did hidradenitis suppurativa affect your ability to do your regular daily activities, other than work at a job?

By regular activities, we mean the usual activities you do, such as work around the house, shopping, child care, exercising, studying, etc. Think about times you were limited in the amount or kind of activities you could do and times you accomplished less than you would like. If hidradenitis suppurativa affected your activities only a little, choose a low number. Choose a high number if hidradenitis suppurativa affected your activities a great deal.

Hidradenitis												Hidradenitis
suppurativa had no effect on my daily activities	0	1	2	3	4	5	6	7	8	9	10	suppurativa completely prevented me from doing my daily activities
CIRCLE A NUMBER												

WPAI:SHP (US English)

HS has a severely negative effect on patients quality of life.^{1,2} It typically presents with painful, deep-seated nodules, which either resolve spontaneously, persist as non-tender nodules, or progress to form abscesses. Abscesses typically rupture and release purulent drainage. Abscesses and nodules may heal with scarring and the formation of fistulas or sinus tracts. Thus, many patients with HS develop permanent sequelae of past inflammation that are only remediable through surgical excision of the involved skin areas. The physical and psycho-social morbidity associated with en bloc excision of scarred axillary, inguinal, or groin skin is substantial. Rare complications of HS include fistula formation into urethra, bladder, rectum, or peritoneum, lymphedema of the limbs or scrotal elephantiasis, and squamous cell carcinomas of the skin originating from HS lesions.

HS affects approximately 1 % of the general population. ^{3,4} Disease onset is typically after puberty. Disease prevalence decreases from 1.5% in those <25 years of age to 0.5% in those older than 55 years of age. It affects women from 2 to 5 times more commonly than men. Several factors may predispose a person to HS, including genetics, cigarette smoking, and obesity.⁵

Compared to other dermatological diseases (e.g. acne psoriasis, atopic eczema and skin tumors) the impact, measured by the Dermatology Life Quality Index (DLQI), is significantly greater. Although this is shown in studies from different parts of the world there is only limited information available on the Quality of Life in Swedish HS patients and there are no national registries capturing this information.

2 Study objectives

2.1 Primary Objectives

The objectives of this observational study is to assess the changes in QoL, skin pain, work productivity/activity and health related problems before and after 6 months treatment with Adalimumab of Swedish patients with moderate to severe HS in reallife and as per routine clinical care.

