3.2 Number of patients

3.2.1 Sample size calculations

With 50 evaluable patients, the power is 90% based on a change in DLQI of -5.4, and an assumed standard deviation of 11.5 and type I error of 5% (two-sided). The dropout rate is considered to be low, approximately 5% after 12 weeks, which will have a minimal impact on the power (decreased to 88%).

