4.3 Effectiveness analysis sets

4.3.1 Full analysis Set (FAS), (modified Intention-to-treat(ITT)

The FAS will include all enrolled patients, with the exception of subjects who were enrolled and not treated with any dose of adalimumab, or who had no baseline or post baseline data collected for the primary endpoint Dermatology Life Quality Index (DLQI). In case all of a patients post baseline assessments of DLQI are outside visit windows, the patient is excluded from FAS.

The FAS will be used for baseline characteristics and analysis of effectiveness.

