4.3.2 Per protocol analysis set (PP)

Criteria for the determination of the PP population will be finalized prior to database lock, and will include the following:

- Study subjects included in FAS
- Study subjects meeting all inclusion criteria and none of the exclusion criteria
- Study subjects with a valid 12 week assessment(according to visit windows) for the primary endpoint Dermatology Life Quality Index
- Study subjects who up until the valid 12 week assessment have less than 4 missed doses of Adalimumab

The PP analysis set will be used as sensitivity analysis for the primary effectiveness endpoint.

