5.2 Secondary endpoints

- Change in DLQI at 4 and 24 weeks
- Change in Patient's Global Assessment of Skin Pain (NRS) at 4, 12 and 24 weeks.

NRS consists of two Visual Analogue Scale response questions :

Patient's response on each question can range from 0 to 10

• Change in items of EuroQol (EQ-5D) at 4, 12 and 24 weeks

EQ-5D consists of 5 sub-items:

Mobility Self-care Usual Activities Pain/Discomfort Anxiety/Depression

each classified into levels 1 to 3 where 3 is most severe.

• Change in EuroQol (EQ-5D) VAS score at 4, 12 and 24 weeks

• Change in items of Hidradenitis Suppurativa Impact Assessment (HSIA) at 4, 12 and 24 weeks.

HSIA consist of 18 sub items of which 16 range from 0 to 10 and 2 items register time at work/school and time away from work/school because of HS.

• Change in Work Productivity and Activity Impairment Questionnaire: Specific Health Problem (WPAI:SHP) at 4, 12 and 24 weeks

The WPAI consists of six questions regarding productivity and impairment: (Q1) Currently employed

- (Q2) Hours missed due to specified problem
- (Q3) Hours missed for other reasons
- (Q4) Hours actually worked
- (Q5) Degree problem affected productivity while working
- (Q6) Degree problem affected regular activities

From above questions, four scores will be calculated: Percent work time missed due to problem: [Q2/(Q2+Q4)]*100Percent impairment while working due to problems: (Q5/10)*100Percent overall work impairment due to problem: $\{Q2/(Q2+Q4) + [(1-(Q2/(Q2+Q4)))*(Q5/10)]\}*100$ Percent impairment while doing regular activities: (Q6/10)*100

• Hidradenitis Suppurativa Clinical Response (HiSCR) at 4, 12 and 24 weeks

HiSCR is a clinical endpoint focusing on assessment of HS inflammatory signs and symptoms that will determine the clinical effectiveness of Adalimumab. HiSCR requires:

- At least a 50% reduction in the total abscess and inflammatory nodule count (AN count) relative to baseline, and
- No increase in abscess count, and
- No increase in draining fistula count.

In first bullet AN count is defined as sum of abcess count and inflammatory nodules count.

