5.3 Safety endpoints

• Non-serious Adverse events

As the safety profile of Adalimumab is stable and well established, non-serious events will not be actively solicited as these events are not likely to further contribute

to the understanding of the safety profile of the product. Any non-serious reports will be collected as spontaneous reports if notified to AbbVie.

• Serious Adverse events

Serious adverse events will be reported to AbbVie from the time the physician obtains the patient's authorization to use and disclose information (or the patient's informed consent) until 30 days or 5 half-lives following the intake of the last dose of physician-prescribed treatment.

In the CRF the response to the following question is registered at 4, 12 and 24 week visits:

Has any SAE(s) occurred since last visit?

6 Analysis Methods

The final statistical analyses will be performed at Scandinavian Development Services AB, Danderyd, Sweden by using the SAS ® version 9.3 or higher.

Continuous variables will be summarized using descriptive statistics (n, mean, SD, min, median, max). Categorical variables will be summarized in frequency tables (frequency and proportion). Graphical presentations, e.g. describing the change over time, will be used as appropriate, and individual patient data will be listed.

The primary and secondary endpoints (change in DLQI, Patient's Global Assessment of Skin Pain (NRS), EQ-5D VAS score and WPAI:SHP at 4, 12 and 24 weeks) will be analyzed using paired samples t-tests or non-parametric methods such as Wilcoxon signed rank test as appropriate.

HiSCR is a dichotomous response variable which will be analysed descriptively presenting proportion HiSCR with binomial exact 95% confidence interval.

The change at 12 weeks will be of primary interest.

Visit windows regarding 4, 12 and 24 weeks assessments following first dose of Adalimumab will decide the validity of assessment.

•	Baseline	Last assessment before first dose of Adalimumab
•	4 weeks	Day $(4*7)$ - $(3*7) \ll 4$ weeks \ll Day $(4*7)$ + $(3*7)$

•	12 weeks	Day (12*7)-(4*7)	<= 12 weeks <= Day (12*7)+(4*7)
•	24 weeks	Day (24*7)-(7*7)	<= 24 weeks <= Day (24*7)+(7*7)

Assessments outside these visit windows will not be part of input for summaries by visit. Such assessments will only be presented in listings.

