6.2.1 Missing data

In general imputation of missing observations will not be performed. Missing data will be reported descriptively.

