6.4 Effectiveness analyses

Effectiveness analyses will be based on the Full analysis Set (FAS), as described in earlier sections, using paired samples t-tests or non-parametric methods such as Wilcoxon signed rank test as appropriate for numerical endpoints. Dichotomous response variables which will be analysed descriptively presenting proportion of responders with binomial exact 95% confidence interval.

The PP analysis set will be used as sensitivity analysis for the primary effectiveness endpoint.

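### The six-month DLQI change is tested only in patients seen at week 24, and no planned analysis quantifies what selective loss would do to it

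*SAP*

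**What the plan says.** The study title refers to quality-of-life change after six months on adalimumab. SAP 2.1 gives one objective, which ends with "health related problems before and after 6 months treatment with Adalimumab of Swedish patients with moderate to severe HS", and SAP 2.2 lists no secondary objectives. Protocol 7.3 adds that evaluation beyond 12 weeks is needed.

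The primary endpoint is DLQI change at 12 weeks (SAP 5.1). SAP 5.2 lists "Change in DLQI at 4 and 24 weeks" as secondary. Both documents say that week 12 is of primary interest.

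For the analysis:

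- The FAS leaves out patients never dosed "or who had no baseline or post baseline data collected for the primary endpoint Dermatology Life Quality Index (DLQI"), and those whose post-baseline DLQI values all fall outside the visit windows (SAP 4.3.1). One in-window post-baseline DLQI is therefore enough for entry.
- Numerical endpoints are tested in the FAS by paired t-test or Wilcoxon signed rank (SAP 6 and 6.4).
- On visit windows, SAP 6 says: "Assessments outside these visit windows will not be part of input for summaries by visit".
- On missing data, SAP 6.2.1 says: "In general imputation of missing observations will not be performed. Missing data will be reported descriptively". No exception is named.
- On sensitivity, SAP 6.4 says: "The PP analysis set will be used as sensitivity analysis for the primary effectiveness endpoint". Membership of that set requires, among other things, "Study subjects with a valid 12 week assessment(according to visit windows") for DLQI (SAP 4.3.2).
- The only dropout figure is "approximately 5% after 12 weeks, which will have a minimal impact on the power" (SAP 3.2.1).

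**The concern.** A paired test at week 24 uses only patients who have a DLQI at baseline and inside the week 24 window. A patient with week 4 and week 12 scores who is not seen at week 24 is in the FAS but contributes nothing to the six-month result. If such patients tended to be those who had improved less, the reported mean would describe a favourably selected group.

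The study has no control group (Protocol 9.9), so selective loss cannot show up as a difference between arms. The per-protocol analysis does not help: it concerns week 12, and it removes patients without a valid week 12 DLQI instead of asking what their absence does. At stake is the size of the six-month change, which answers the title and objective and which Protocol 7.3 links to reimbursement.

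**Working it through.** **1. The plan's own figure.** Inputs from SAP 3.2.1: change -5.4, SD 11.5, two-sided 5%, n = 50. For a one-sample t-test on change, the non-centrality is (5.4/11.5) × √n.

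- n = 50: 0.4696 × 7.071 = 3.32, power 90.2%.
- n = 47 (5% dropout, rounded down): 0.4696 × 6.856 = 3.22, power 88.3%. With n = 48 it is 89.0%.

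The stated 90% and 88% reproduce. They belong to week 12.

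**2. Size of the bias if loss depends on week 12 response.** The documents give no week 24 retention, so everything here except -5.4 and 11.5 is assumed. The set-up is 47 patients with week 12 data; normally distributed week 12 and week 24 changes with correlation ρ of 0.5 or 0.8; and odds of being missing at week 24 multiplied by 2 or 3 for each SD of worse week 12 change. Each cell has 20,000 simulated studies. The floor and ceiling of the DLQI are not modelled. The true week 24 change is -5.4.

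| Missing at week 24 | Odds ratio | Mean in observed patients (ρ 0.5 / 0.8) | Overstatement | Coverage of 95% CI |
|---|---|---|---|---|
| 10% | 2 | -5.80 / -6.02 | 0.40 / 0.62 | 94.4% / 93.7% |
| 20% | 2 | -6.17 / -6.58 | 0.77 / 1.18 | 93.1% / 90.4% |
| 30% | 2 | -6.50 / -7.13 | 1.10 / 1.73 | 91.9% / 86.4% |
| 30% | 3 | -6.94 / -7.89 | 1.54 / 2.49 | 88.2% / 75.3% |

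At 5% missing and odds ratio 2, the overstatement is 0.2 to 0.3 points.

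These values are consistent with the mechanism: overstatement ≈ ρ × 11.5 × (shift in mean week 12 change among those who stay, in SD). At 20% missing, 0.77/(0.5 × 11.5) = 0.13 and 1.18/(0.8 × 11.5) = 0.13, the same shift from both correlations.

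**3. What using week 12 data achieves.** Regressing week 24 on week 12 change in observed patients and averaging over all 47 gives the mean that an unstructured repeated-measures model gives for these two visits. In every cell above it returns -5.38 to -5.42 with coverage of 95.0 to 95.6%. That is expected, because dropout was generated from week 12 change, which is the model's own assumption. When dropout depends on the unseen week 24 change instead (10 to 30% missing, odds ratio 2 to 3), the model-based mean is about -5.7 to -7.8. In the worst of these cells (30%, odds ratio 3, ρ 0.5) it is -7.8, against -8.5 in observed patients.

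**4. Zero change for the missing.** If observed patients average -5.4 and the others are given zero, with 50 in the FAS:

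- 45 observed: -5.4 × 45/50 = -4.86 (95% CI -7.99 to -1.73).
- 40 observed: -5.4 × 40/50 = -4.32 (-7.30 to -1.34).
- 35 observed: -5.4 × 35/50 = -3.78 (-6.59 to -0.97).

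**The case against.** Week 24 DLQI is openly secondary, and week 12 is of primary interest. The title and objective concern quality of life and related outcomes, not DLQI alone, which is one of three quality-of-life scales. The only retention figure in the documents is 5% lost by week 12. A similar further loss would put week 24 at or below the mildest row of the table, where the bias is small. The week 24 window is wide (day 168 ± 49), so few visits should fall outside it. Missing data are to be described, withdrawal reasons and individual data listed, and disposition tabulated, so an attentive reader could look up the week 12 scores of patients absent later. Well patients might also be the ones who skip visits, which would reverse the sign of the bias.

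All of this stands, and it limits the size of the point. It does not remove it: listings may hint at selective loss but do not say how far the week 24 mean would move, and the plan does carry out inferential tests at week 24.

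Three stronger readings are tempting and are not supported:

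- A reader might infer that the SAP leaves open whether a DLQI recorded after stopping adalimumab counts. It does not. Windows run from the first dose with no on-treatment condition, and effectiveness uses the FAS, so an in-window value counts.
- A reader might infer that the sample size is deficient because week 24 retention and power are not given. For a declared secondary endpoint, that is a matter of preference.
- A reader might take the HiSCR non-response rates in Protocol Table 16 as a guide to week 24 loss. No document links non-response to missing visits.

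**Conclusion.** The point holds as a cheap improvement to a secondary analysis, not as an error in the primary one. The week 24 DLQI result has no missing-data check, and DLQI already collected at weeks 4 and 12 could supply one.

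If loss favours better responders, the likely overstatement is 0.2 to 0.6 points with coverage near 94% at 5 to 10% missing, and 0.8 to 1.2 points with coverage of 90 to 93% at 20%. The 30%, odds ratio 3 row (1.5 to 2.5 points, coverage 75 to 88%) is a stress case in which several unfavourable assumptions meet, and it should not be read as a forecast. All retention, odds-ratio and correlation values are assumptions. If dropout is unrelated to response, there is no bias.

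**What to change.** Add to SAP 6.2.1 and 6.4:

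1. A supportive mixed model for repeated measures on DLQI change at weeks 4, 12 and 24 in the FAS, with visit, baseline DLQI and unstructured covariance. Report the week 24 and week 12 means with 95% CIs beside the paired tests.
2. A table of mean week 12 DLQI change in FAS patients with and without an in-window week 24 DLQI.
3. Optionally, the week 24 mean with zero change assigned to FAS patients lacking that assessment. Call it a pessimistic scenario and not a bound, since patients can worsen.

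The primary endpoint, the significance level and the no-adjustment rule stay as they are.

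The cost is a short SAP amendment before final database lock and some programming; no new data are needed. The model assumes that dropout depends only on observed DLQI and stays partly biased if it depends on unseen week 24 values, so it is supportive only. If few patients are missing, the results will nearly agree. The planned interim DLQI listings stop at week 12, but SAP 6.1.5 relaxes access to interim data for staff who may work on the SAP. The amendment should therefore be dated and should state whether week 24 DLQI has been seen.
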